## 9.3 Pediatrics Quality of Life Questionnaire (PedsQL)

The pediatrics quality of life questionnaire (PedsQL) is a generic HRQoL instrument designed specifically for a pediatric population. The questionnaire consists of different questions based on the age of the subjects for ages 2-4, 5-7 and 8-12. The PedsQL capture data for the following domains: physical functioning, emotional functioning, social functioning, school functioning, psychosocial functioning, physical health and a total score.

Information on the PedsQL is to be obtained from electronic patient diaries.

The questions in the PedsQL are categorized as set out in Table 4.

**Table 4 Categorizing Pediatric Quality of Life Questions** 

Category	Toddler	Young Children	Child Report
(Problems with)	(Ages 2 -4)	(Ages 5-7)	(Ages 8-12)
Physical	Walking	Walking 100	It is hard for me to
Functioning		meters	walk more than a
			couple of streets
			(100 meters)
	Running	Running	It is hard for me to
			run
	Participating in	Participating in	It is hard for me to
	active play and	sports activities or	do sports activities
	exercise	exercise	or exercise
	Lifting heavy	Lifting something	It is hard for me to
	things	heavy	lift heavy things
	Bathing	Taking a bath or	It is hard for me to
		shower by him or	have a bath or
		herself	shower by myself
	Helping to pick up	Doing chores, like	It is hard for me to
	his or her toys	picking up his or	do chores around
		her toys	the house
	Having aches or	Having aches or	I have aches and
	pains	pains	pains
	Feeling tired	Feeling tired	I feel tired.
Emotional	Feeling afraid or	Feeling afraid or	I feel afraid or
Functioning	scared	scared	scared

Category	Toddler	Young Children	Child Report
(Problems with)	(Ages 2 -4)	(Ages 5-7)	(Ages 8-12)
	Feeling sad	Feeling sad	I feel sad
	Feeling angry	Feeling angry	I feel angry
	Having trouble	Trouble sleeping	I have trouble
	sleeping		sleeping
	Worrying	Worrying about	I worry about what
		what will happen to	will happen to me
		him or her	
Social Functioning	Playing with other	Getting on with	I have trouble
	children	other children	getting on with
			other children
	Other children not	Other children not	Other children do
	wanting to play	wanting to be his or	not want to be my
	with him or her	her friend	friend
	Getting teased by	Getting teased by	Other children tease
	other children	other children	me
	Not able to do	Not being able to	I cannot do things
	things that other	do things that other	that other children
	children his or her	children his or her	my age can do
	age can do	age can do	
	Keeping up when	Keeping up when	It is hard to keep up
	playing with other	playing with other	when I play with
	children	children	other children
Nursery/Day Care	Doing the same		
Functioning	nursery/day care		
	activities as my		
	peers		
	Missing nursery		
	day/care because of		
	not feeling well		
	Missing		
	nursery/day care to		
	go to the doctor or		
	hospital		
School		Paying attention in	It is hard to pay
Functioning		class	attention in class

Category	Toddler	Young Children	Child Report
(Problems with)	(Ages 2 -4)	(Ages 5-7)	(Ages 8-12)
		Forgetting things	I forget things
		Keeping up with	I have trouble
		school activities	keeping up with my
			school work
		Missing school	I miss school
		because of not	because of not
		feeling well	feeling well
		Missing school to	I miss school to go
		go to the doctor or	to the doctor or
		hospital	hospital

Each question of the PedsQL is to be scored as follows:

Never: 100

Almost never: 75Sometimes: 50

• Often: 25

Almost always: 0

Scores for the categories of physical functioning, emotional functioning, social functioning and school functioning are to be derived as the mean of the individual question scores of available data. Missing data are not to be imputed. At least half of the questions in a particular score category needs to be answered for a score to be presented.

The psychosocial health summary score is to be derived as the mean of the individual questions for the emotional functioning, social functioning and school functioning categories. The physical health summary score is to be set equal to the physical functioning category score.

The PedsQL scores and changes from baseline are to be summarized for the FAS by treatment regimen and age category. The number of subjects with an improvement (defined as an increase in PedsQL score greater than 1) are to be presented for the FAS. A Wilcoxon test for paired samples is to be presented on the FAS comparing the baseline and study completion scores for any statistical significant differences using the SAS code provided in Section 9.1: Haemophilia Symptom Questionnaire (Haemo-Sym).

PedsQL individual results and calculated scores are to be listed for the FAS.

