10.5.2 Patient Reported Outcomes

The following PROs will be assessed at the start of prophylaxis treatment, every 6 months and at the end of study visit:

- Bleed and pain severity will be measured using the Haemo-SYM for subjects ≥ 18 years of age
- HRQoL will be assessed using the Short Form 36 (SF-36) for subjects ≥ 14 years of age
- HRQoL will be assessed using the Pediatric Quality of Life Inventory™ (PedsQL^{xiii}) for subjects < 14 years of age (for subjects aged ≥ 8 to < 14 years, the PedsQL Child report (23 items) will be completed; for subjects aged ≥ 5 to < 8 years, the PedsQL Parent report (23 items) will be completed; for subjects aged ≥ 2 and < 5 years, the PedsQL Parent report (21 items) will be completed; for subjects aged < 2 years, the PedsQL is not used)
- Patient satisfaction with treatment will be assessed using the Satisfaction Questionnaire (for subjects aged ≥ 12 years, the subject completes the questionnaire; for subjects aged < 12 years, the caregiver completes it on behalf of the subject)
- Patient Activity Level (for subjects aged ≥ 12 years, the subject completes the assessment; for subjects aged < 12 years, the caregiver completes it on behalf of the subject)

xiiiNOTE: Patients should be given the same questionnaire at follow-up that they were given at baseline, even if they move up an age range during the study.

Details on each of the PROs are as follows:

- **Haemo-SYM Questionnaire** – This is a self-administered, validated questionnaire designed to assess symptom severity in patients with hemophilia. This measure contains 17 items and includes 2 domains: Bleeds and Pain. Scores for each of these 2 domains can be calculated, with higher scores indicating more severe symptoms.
- **SF-36** – The SF-36 is a self-administered, validated questionnaire designed to measure generic HRQoL. This 36-item questionnaire measures 8 domains, including: Physical functioning, Role-physical, Bodily pain, General health, Vitality, Social functioning, Role emotional, and Mental health. Two summary scores can be calculated, the Physical Component Score, and the Mental Component Score. Additionally, scores can be calculated for each of the 8 domains. Higher scores indicate better health status.

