- **PedsQL** – The PedsQL is a generic HRQoL instrument designed specifically for a pediatric population. Depending on the subject's age, the PedsQL contains 23 (for subjects aged ≥ 5 to < 14 years) or 21 (for subjects aged ≥ 2 to < 5 years) items and measures 7 domains: Physical Functioning, Emotional Functioning, School Functioning, Social Functioning, Psychosocial Summary, Physical Health, Total Score. Higher scores indicate better health status.
- **Patient Satisfaction Questionnaire** – This questionnaire is a non-validated measure that assesses the subject's (or via their caregiver) level of satisfaction with their treatment. For BAX 855 naïve subjects and BAX 855 naïve surgery subjects^{xiv}, at the end of study visit, the questionnaire also assesses the subject's preference between his previous treatment prior to the study and BAX 855. This questionnaire will be administered to all age groups.
- **Patient Activity Level** – Subjects will also be asked to estimate their activity levels. This will consist of a few questions asking subjects (or their caregiver) to rate their current level of activity. These data will be collected for all age groups.

xiv ie, subjects transitioning from the surgery study (Study 261204) into this continuation study that were naïve to BAX 855 prior to entry into the surgery study.

In addition, the following will be collected where applicable, for each occurrence:

- **Health Resource Use** – The subject (or their caregiver) will record the following events: (1) days missed from work/school (as appropriate) and days not able to perform normal activities outside of work/school due to hemophilia, (2) physician office visits, (3) hemophilia treatment site visits, (4) emergency room visits (reason and number), and (5) hospitalizations (reason, dates of hospitalization and associated length of stay). These data will be collected for all age groups.

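### The PedsQL scoring in SAP 9.3 assigns the three nursery/day-care items of the age 2-4 form to no category or summary score, so the toddler psychosocial summary uses 10 of its 13 items

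*SAP*

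**What the plan says.** Protocol 10.5.2 uses the PedsQL in children under 14. For ages 2 to <5, "the PedsQL Parent report (21 items) will be completed". The form lengths are "23 (for subjects aged ≥ 5 to < 14 years) or 21 (for subjects aged ≥ 2 to < 5 years) items". The same sentence covers both lengths and goes on: "items and measures 7 domains: Physical Functioning, Emotional Functioning, School Functioning, Social Functioning", followed by the psychosocial, physical health and total scores. It names no nursery domain. A footnote in that section keeps a child on the baseline questionnaire at follow-up even after the child moves up an age range.

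SAP 9.3, Table 4, sorts the items by category for three forms (ages 2-4, 5-7 and 8-12). The age 2-4 column has a category of its own, "Nursery/Day Care" Functioning, with three items: joining in the same activities as peers, absence through feeling unwell, and absence for a doctor or hospital visit. The School Functioning cells of that column are empty.

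The scoring text after the table gives every question a value from 0 to 100. It derives category scores as item means for physical, emotional, social and school functioning, and defines the psychosocial summary as the "mean of the individual questions for the emotional functioning, social functioning and school functioning categories". The physical health summary equals the physical category score. Nursery/day care is not mentioned again. A total score is listed as a domain at the start of 9.3 but has no formula. Improvement is an increase of more than 1 point, and change from baseline to study completion is tested with a paired Wilcoxon test.

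**The concern.** A programmer who follows 9.3 as written has no score in which to place the three nursery items. Two consequences follow for the age 2-4 form. The psychosocial summary is built from emotional and social items alone. The school domain, which the protocol attributes to both form lengths, does not exist for these children.

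Two of the three omitted items ask about absence through illness or medical visits. The matching school items are kept for older children, so one score label covers different content by age.

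Change in PedsQL is a named secondary outcome with a significance test and a responder count. At stake are its ability to register change in the youngest children and the meaning of level summaries in rows that mix forms. Neither co-primary outcome is affected.

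**Working it through.** **Inputs.** Item counts come from SAP Table 4, form lengths from Protocol 10.5.2, and response values (steps of 25 from 0 to 100) and the improvement threshold (>1) from SAP 9.3. No document gives item means.

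**Step 1: reproduce the form lengths.**

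| Category | Ages 2-4 | Ages 5-7 and 8-12 |
|---|---|---|
| Physical | 8 | 8 |
| Emotional | 5 | 5 |
| Social | 5 | 5 |
| Nursery/day care | 3 | 0 |
| School | 0 | 5 |
| Total | 21 | 23 |

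Both totals match the protocol, so Table 4 is complete and the three nursery items are needed to reach 21.

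**Step 2: items in the psychosocial summary as written** (emotional + social + school).
- Ages 2-4: 5 + 5 + 0 = 10, out of 21 - 8 = 13 non-physical items (76.9%).
- Older forms: 5 + 5 + 5 = 15, out of 23 - 8 = 15 (100%).

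**Step 3: sensitivity to change.** All items are assumed answered. If one nursery item moves by one response category (25 points) and nothing else changes:
- the 13-item summary moves by 25/13 = 1.92, which exceeds 1, so a rise counts as improvement;
- the 10-item summary moves by 0, so it does not.

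If all three nursery items move by one category, the 13-item summary moves by 75/13 = 5.77 and the 10-item summary still by 0.

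**Step 4: difference in level.** Let d be the mean of the ten emotional and social items minus the mean of the three nursery items. With M the mean of the ten:

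10-item score - 13-item score = M - [10M + 3(M - d)]/13 = (3/13) x d

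| Assumed d | Offset (points) |
|---|---|
| 5 | 1.2 |
| 25 | 5.8 |

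For example, M = 75 with a nursery mean of 50 (d = 25) gives 75.0 on ten items and 69.2 on thirteen. If d is negative the sign reverses, and at d = 0 there is no offset.

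**Step 5: where levels are combined across forms.** PedsQL summaries are by regimen and age category. The age bands in SAP 5.11 do not follow the forms: the EU band under 6 spans the 2-4 and 5-7 forms, and the US band 2 to <12 spans all three. Within those rows the psychosocial score mixes a summary without any school or nursery content and one with it.

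**Step 6: paired change.** By Step 4, the change on ten items differs from the change on thirteen by (3/13) x (d at completion - d at baseline). If d is constant the offset cancels. What remains is exactly the change in the nursery items relative to the others, which is the loss shown in Step 3.

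**The case against.** **The intended reading is obvious.** The protocol lists School Functioning for the 21-item form, and two nursery items mirror the items on missing school. A programmer could well treat nursery as the toddler version of school. That is plausible, and it supports the proposed fix. But Table 4 lists the two as separate categories and the scoring text names only one of them, so the literal instruction gives the shorter score.

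**The items are not ignored.** Every question receives a value and individual results are listed. That stands: what is missing is their assignment to any category or summary score.

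**A change of form.** A reader might infer that a child who starts on the age 2-4 form and later answers the 5-7 form would show a spurious change. The documents do not support this. The Protocol 10.5.2 footnote keeps the baseline questionnaire at follow-up. It speaks of moving up an age range during the study and does not expressly address a baseline taken in a parent study, but nothing in the documents provides for a switch.

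**Bias in the Wilcoxon test.** A reader might also infer that the level offset biases the paired test. It does not if d is constant, by Step 6.

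**Scope.** This is one domain and one summary of a secondary patient-reported outcome, in the youngest children only. That is correct and limits the weight of the point. The undefined total score is a wider gap, since it affects every form.

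**Conclusion.** The point holds as a scoring omission. Under SAP 9.3 as written, three of the 13 non-physical items on the age 2-4 form enter no defined category or summary score, toddlers have no school-domain score, and the missing total-score formula leaves open whether it uses 18 (8 + 10) or 21 items.

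The firm consequence is lost sensitivity: a one-category change in one nursery item is worth 1.92 points on a 13-item summary and 0 on the 10-item one, on either side of the >1 threshold. This rests only on the item counts, the response values and complete answers.

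The level offset of (3/13) x d is conditional. Neither the size nor the sign of d is in the documents, so 1.2 and 5.8 points are illustrations, relevant to level summaries in rows that mix forms. Calling the 10-item score too high would assume both that d is positive and that the 13-item score is the right reference. Neither a within-child form-switch effect nor a biased paired test is shown.

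**What to change.** Add to SAP 9.3: for the age 2-4 form, the three nursery/day-care items form the School Functioning score and enter the psychosocial summary (13 items) and the total score (21 items). State the total-score formula for every form as the mean of all items on the form. State that parent-study baselines are scored by the same rules, so that both ends of each change score use the same items. The existing rule that at least half of a category's items be answered would then require two of the three nursery items for a School Functioning score.

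The cost is a short SAP addition and a change to the scoring program. No new data are needed, because the items are already on the form.

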#### 10. EVALUATION OF EXPLORATORY OUTCOME MEASURES

#### **10.1** Patient Satisfaction Questionnaire

The patient satisfaction questionnaire is a non-validated measure that assesses the subject's level of satisfaction with their treatment. For BAX 855 naïve subjects and BAX 855 naïve surgery subjects, at the end of study visit, the questionnaire also assesses the subject's preference between his previous treatment prior to study and BAX 855.

Frequency statistics and listings on patient satisfaction questionnaire results are to be presented for the FAS.

## 10.2 Patient Activity Level

Patient activity levels are to be summarized and listed for the FAS.

## 10.3 Hospitalizations Due to Hemophilia A

Information on hospitalizations is to be obtained from the eCRF (*Other Hospitalizations* eCRF panel).

The following derivations based on eCRF reported results are to be performed:

Duration of hospitalization in days:
 Duration(Days) = (End Date of Hospitalization - Start Date of Hospitalization) + 1

Annualized number of hospitalizations and annualized duration of hospitalizations in days are to be summarized by treatment group and age group for the SAS. All hospitalizations are to be listed for the SAS.

Results are to be annualized by dividing the OPE in years of each subject with results obtained during the course of the study.

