$$OPE(Weeks) = \frac{OPE(Days)}{365.2425} \times 52$$

• The OPE in months is to be determined from the OPE in days as:

$$OPE(Months) = \frac{OPE(Days)}{365.2425} \times 12$$

• The OPE in years is to be determined from the OPE in days as:

$$OPE(Years) = \frac{OPE(Days)}{365.2425}$$

- All OPE calculations to be performed overall and per treatment regimen.
- The average number of infusions per time period (weeks, months, years) is to be determined as the total number of infusions during the observation period divided by the duration for the particular time period (weeks, months, years).
- Total dose (IU/kg or IU as applicable) is to be determined as the sum of all doses, overall and by reasons for infusion, during the observation period in the current study.
- The average dose per time period (weeks, months, years) is to be determined as the total dose (IU/kg or IU as applicable) the subject received during the observation period in the current study, divided by the duration for the particular time period (weeks, months, years).
- Average dose per bleed is determined as the sum of all doses (IU/kg or IU as applicable) given to treat bleeding episodes divided by the number of bleeds observed for the particular subject in the current study.

Extent of exposure is to be summarized using descriptive statistics for the SAS, and PPAS and listed for the SAS. Summaries are to be presented by age category and treatment regimen at time of dose.

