- A bleed is considered to be a minor bleed if the severity is indicated as "Mild" or "Minor".
- A bleed is considered to be a weekday bleed if the bleed occurred on a Monday, Tuesday, Wednesday, Thursday or Friday.
- A bleed is considered to be a weekend bleed if the bleed occurred on a Saturday or Sunday.
- A bleed is considered to be a morning bleed if the bleed occurred between 04:00 and 11:59.
- A bleed is considered to be an afternoon bleed if the bleed occurred between 12:00 to 17:59.
- A bleed is considered to be a night bleed if the bleed occurred between 18:00 and 03:59.
- A bleed is considered to have occurred at an unknown time if the time of a bleed is not available.
- Time since last prophylactic infusion in hours is to be derived as:
  - $Time(h) = Date/Time\ of\ Bleed\ Start\ Date/Time\ of\ Infusion$  where the start date/time of infusion refers to the last prophylactic infusion received (other than to treat a bleed) prior to the start of the bleed. Time since last prophylactic dose is to be categorized as:
    - $\circ$  <24 hours.

```
24 - <48 hours.

48 - <72 hours.

72 - <96 hours.

>96 hours.
```

• Time since previous bleed are only to be determine if a subject had multiple bleeds and is to be derived as:

```
Time(months)
= (Date/Time \ of \ Current \ Bleed
- Date/Time \ of \ Previous \ Bleed)/365.2425 \times 12
```

- A bleed is considered to be treated with BAX 855 if at least one infusion linked to the particular bleed is present in the *Study Infusion* eCRF panels. Infusions to "Maintain Hemostasis" are not to be summarized as part of treatment for bleeding episodes.
- The number of bleeds per subject overall and by location (target joint, non-target joint, joint and non-joint), causality (spontaneous/unknown and injury), severity (mild, moderate and severe) and timing (weekends, weekdays, morning, evening and afternoon) are to be determined as the count of unique bleeds in each category a subject had during the observation period.
- Annualized bleeding rate (ABR) is to be derived for each treatment regimen the subject had during the study as:

$$ABR = \frac{Number\ of\ unique\ bleeds}{OPE\ (years)\ for\ treatment\ regimen}$$

The ABR is to be analyzed using a generalized linear model fitting a negative binomial distribution with logarithmic link function. Only subjects that have 100 or more EDs are to be included in the models, where total EDs are derived as in Section 6.7: Extent of Exposure.

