- An AE is considered severe if the eCRF question "Severity" is answered "Severe".
- An AE is considered related as assessed by the Investigator if the AE is indicated as "Possibly related" or "Probably related" in the eCRF. An AE is considered unrelated as assessed by the Investigator if the AE is indicated as "Not related" or "Unlikely related" in the eCRF.
- An AE is considered related as assessed by the Sponsor if the Sponsor Medic deem the AE related to the study medication. Prior to any analyses described in this SAP, a list of all AEs in the database is to be provided to the Sponsor Medic to assess relationship from a Sponsor perspective of AE to study medication.
- An AE is considered leading to discontinuation of study medication if indicated as "Drug withdrawn" in the eCRF.
- An AE is considered leading to discontinuation of study if the AE is indicated as the primary reason why the subject did not complete the study from the *Study Completion/Termination* eCRF panel.
- An AE is considered as leading to death if the question "Did the serious event result in death" is indicated as "Yes" or if the outcome in the eCRF is indicated as "Fatal".
- An AE is considered to be an allergic reaction if the question "Was this event considered to be an allergic reaction" is indicated as "Yes".
- An AE is considered to be a thrombotic event if the question "Is this a thrombotic event" is indicated as "Yes" in the eCRF.

AEs that occurred during or after BAX 855 are to be presented for the SAS. Summary tables are to indicate the number of subjects who experienced AEs as well as the number of AEs. Summaries for BAX 855 as indicated in the latest version of the Output Templates are also to include the rate of AEs per 100 infusions and rate of AEs per year. In addition, tables are to be prepared to summarize each AE by system organ class and preferred term, the number of subjects who experienced an AE at least once, the rate of subjects with AE(s), AEs per 100 infusions and AE rate per year. AE summaries by seriousness, severity and relationship are to be presented as well.

AE rate per 100 infusions is to be determined as the number of AEs divided by the total number of infusions (regardless of the reason the infusion was administered) in the study multiplied by 100.

AE rate per year is to be determined as the number of AEs divided by the OPE in years in the current study across all subjects.

All AEs for each subject, are to be listed for the SAS.

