#### **10.4** Health Resource Use Other Than Hospitalizations

Information on health resource use including days unable to go to school/work, days unable to carry out usual activities, number of physician visits, number of clinical visits and number of emergency room visits are to be reported in electronic subject diaries.

Results are to be annualized by dividing the OPE in years of each subject with results obtained during the course of the study.

Information on other health resource usage is to be summarized for the FAS and listed for the SAS.

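### SAP 10.3 and 10.4 state the annualisation rule with numerator and denominator swapped, giving years per event instead of events per year

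*SAP*

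**What the plan says.** SAP 10.3 defines what is to be reported for hospitalisations: "Annualized number of hospitalizations and annualized duration of hospitalizations in days are to be summarized by treatment group and age group". It gives a formula for the length of a single stay, but the annualisation itself rests on one sentence: "Results are to be annualized by dividing the OPE in years of each subject with results obtained during the course of the study".

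SAP 10.4 covers days lost from school, work or usual activities, together with visit counts: "number of physician visits, number of clinical visits and number of emergency room visits are to be reported in electronic subject diaries". Its annualisation rule uses the same sentence, beginning "Results are to be annualized by dividing the OPE in years of each subject with results obtained". Neither section adds a formula or an example for this step.

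The OPE in years is defined in SAP 6.7 as OPE in days divided by 365.2425.

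Elsewhere the SAP forms rates the other way round:

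- SAP 7.1: "Annualized bleeding rate (ABR) is to be derived for each treatment regimen the subject had during the study as" is followed by a formula with unique bleeds over OPE in years for the regimen.
- SAP 8.1: the yearly adverse event rate is "determined as the number of AEs divided by the OPE in years in the current study".
- SAP 6.7: average infusions and average dose per week, month or year are totals divided by duration.

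**The concern.** To divide A with B is, in ordinary usage, to compute A/B. Here A is the OPE in years and B is the subject's result, so the sentence specifies OPE/result. That quantity has the wrong unit (years per hospitalisation, or years per day in hospital) and the wrong direction, because heavier use gives a smaller number. For a subject with no event it is a division by zero.

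If the sentence were programmed as it stands, the tables by treatment group and age group in SAP 10.3 would show the heavier users with the lower values under a label that says annualised number. Subjects with no use would have no value. SAP 5.4 does not impute missing data outside its listed exceptions, and SAP 5.8 reports unavailable quantitative results as a separate category, so those subjects would probably be left out of the means and medians.

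**Working it through.** **Inputs.** The OPE conversion comes from SAP 6.7: OPE (years) = OPE (days) / 365.2425. The documents give no hospitalisation or visit frequencies, so the counts below are assumptions. An OPE of 182 days is also assumed; it lies inside the planned participation of about 3 to 12 months (Protocol 8.3, SAP 6.1). The plan gives no figure of its own to reproduce here.

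**Formulas.**

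- Rule as written in SAP 10.3 and 10.4: OPE (years) / result.
- Form used in SAP 6.7, 7.1 and 8.1: result / OPE (years).

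**Numbers.** 182 / 365.2425 = 0.4983 years.

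| Result in 182 days | As written: 0.4983 / result | Rate: result / 0.4983 | Rate ÷ as written |
|---|---|---|---|
| 0 | undefined | 0 | – |
| 1 | 0.498 | 2.01 | 4.03 |
| 2 | 0.249 | 4.01 | 16.1 |
| 4 | 0.125 | 8.03 | 64.4 |
| 10 (for example, hospital days) | 0.050 | 20.07 | 403 |

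The rate rises down the table while the written rule falls.

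**Dependence on follow-up.** The two forms differ by the factor (result / OPE)², so they agree only when the result equals the OPE in years. One event in 365 days gives 0.999 against 1.001. With longer follow-up and few events the discrepancy changes sign: 1 event in 730 days (1.9987 years) gives 1.999 as written against a rate of 0.500. The error is therefore not a constant multiple that could be divided out.

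**Effect on summaries.** Take two subjects with 182 days each, one with 1 event and one with 4.

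- Mean rate: (2.01 + 8.03) / 2 = 5.02 per year.
- Mean of the values as written: (0.498 + 0.125) / 2 = 0.311, whose reciprocal is about 3.21.

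A reader who suspected the inversion could not recover the mean rate from the summary table by inverting it.

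**The case against.** The strongest reply is that this is awkward wording whose intent is plain. SAP 10.3 names its outputs as an annualised number and an annualised duration, which OPE/result cannot be. The SAP's other rates over time are all built the right way round. A programmer would probably compute result/OPE without a second thought, and one who followed the sentence literally would be likely to meet a division by zero early on. The individual hospitalisations and other resource-use data are also listed, so an error could be found and recomputed. All of this stands, and it limits the practical risk. It does not make the sentence right: the SAP is the specification, the sentence appears in two sections, and nothing in either one corrects it.

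Three stronger readings are tempting, and the documents do not support them.

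- A reader might infer that a whole exploratory objective is reversed. The first exploratory objective also covers patient satisfaction and activity levels, which this rule does not touch. The resource-use data are only to be summarised descriptively and listed (Protocol 13.4.6), with no test or decision resting on them.
- A reader might infer that a large share of subjects would drop out as zero-event cases. That may be so, but the documents give no event frequencies from which to say how many.
- A reader might conclude that every subject without a recorded event should be set to 0. The SAP 10.4 items come from electronic diaries, and a subject without entries may have missing data rather than no use. Setting all of these to 0 would be an imputation that SAP 5.4 does not allow for, and it could bias resource use downward.

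**Conclusion.** The rule in SAP 10.3 and 10.4 is wrong as written. It yields years per event, moves opposite to resource use, is undefined at zero, and contradicts the SAP's own convention in 6.7, 7.1 and 8.1. The conclusion about form and direction rests only on the text. The sizes (0.249 against 4.01 for 2 hospitalisations in 182 days; 0.050 against 20.07 for 10 hospital days) rest on assumed counts and follow-up and are illustrations.

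The consequence is confined to descriptive summaries of hospitalisations and other health resource use, which are one part of the first exploratory objective. The spontaneous bleed rate, inhibitor development and all secondary outcomes are derived by other rules and are unaffected. The correction is worth making because the specification should not depend on a programmer disregarding it.

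**What to change.** In both SAP 10.3 and SAP 10.4, replace the annualisation sentence with: annualised value = number of events (or days) divided by the subject's OPE in years. This is the convention that the SAP already uses for bleeds, adverse events, infusions and dose.

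Add one clause: subjects observed to have no events have a value of 0, and subjects with missing diary data remain missing.

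The cost is two sentences in the SAP. No data collection, analysis set or other derivation changes.
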